## 9.5.2.2. Relationship of Adverse Events to Study Conduct

The relationship of AEs to study conduct will be assessed by the blinded investigator, and will be a clinical decision based on all available information. The following question will be addressed:

Is there a reasonable possibility that the AE may have been caused by study conduct?

The possible answers are:

**Not Related:** There is no reasonable possibility that the event may have been caused by study conduct.

**Related:** There is a reasonable possibility that the event may have been caused by study conduct.

The investigator should justify the causality assessment of each SAE.

A list of factors to consider when assessing the relationship of AEs to study drug is provided below. Please note that this list is not exhaustive.

Is there a reasonable possibility that the event may have been caused by the study conduct?

No:

- due to external causes such as environmental factors or other treatment(s) being administered
- due to the patient's disease state or clinical condition
- do not follow a reasonable temporal sequence following the course of the study.
- do not reappear or worsen when dosing with study participation is resumed

Yes:

- could not be explained by environmental factors or other treatment(s) being administered
- could not be explained by the patient's disease state or clinical condition
- follow a reasonable temporal sequence following the course of the study.
- resolve or improve after discontinuation from study participation.
- reappear or worsen when study participation is resumed

## 9.6. Safety Monitoring

The investigator will monitor the safety of study patient at his/her site(s) as per the requirements of this protocol and consistent with current Good Clinical Practice (GCP). Any questions or concerns should be discussed with the sponsor in a timely fashion. The sponsor will monitor the safety data from across all study sites. The medical monitor will have primary responsibility for the emerging safety profile of the compound, but will be supported by other departments (eg, Pharmacovigilance and Risk Management; Biostatistics and Data Management). Safety monitoring will be performed on an ongoing basis (eg, individual review of SAEs) and on a periodic cumulative aggregate basis.

## 9.6.1. Monitoring Adverse Events of Special Interest

## 9.6.1.1. Adjudicated Arthropathy

Adjudicated arthropathy is an umbrella term that encompasses the following conditions:

- Rapidly progressive OA type 1 and 2
- Subchondral insufficiency fractures
- Primary osteonecrosis

In addition, AAs will be evaluated to determine if they meet the criteria for destructive arthropathy.

Potential events of AA will be monitored via clinical signs and symptoms of worsening joint pain during the course of the study (eg, by applying adverse experiences, the joint pain questionnaire and imaging) as well as scheduled imaging and pre-operative imaging, if a patient requires a joint replacement during the study.

Clinically significant worsening of joint pain during the course of this study is characterized as a worsening of pain in any joint that occurs in spite of treatment with analgesics, is in the opinion of the investigator inconsistent with the normal progression of OA, and is at least 2 weeks duration (or less than 2 weeks if deemed clinically significant at the discretion of the investigator).

If a patient reports an increase in pain as described above, study drug administration will be withheld while imaging of the affected joint, as well as any additional imaging deemed appropriate to understand the cause of the worsening pain, is performed (Section 8.2.3.8). A decision to perform imaging after patient reporting of worsening joint pain will be documented in the respective case report form (CRF) page. Images, along with any other radiographic evaluation, will be submitted to the adjudication committee for review (Section 5.3.2). The investigator may consider aspiration of synovial fluid for further analysis such as cell count and crystal analysis.

If routine imaging suggests the presence of one of the types of AA, study drug administration will be withheld. Any additional imaging deemed appropriate will be obtained. The images, along with results of any other radiographic evaluation, will be submitted to the Adjudication Committee for review (Section 5.3.2).

If the adjudication does not confirm the presence of AA, according to the adjudication criteria, study drug may be restarted.

Study drug dosing will be terminated for patients with findings that suggest AA, and the patients will be referred for orthopedic consultation. If presence of AA is confirmed by the adjudication committee, the case must be reported as an AESI (Section 9.3.3 and Section 9.4.3).

Any patient whose study drug is discontinued due to an AA should be encouraged to return to the clinic for all remaining study visits. Prior to the scheduled JR, the patient should complete the pre-operative study visit (Section 8.2.3.10) and, after the JR, should complete the week 4 and week 20 post-operative study visits (Table 3). Pre-operative images, along with any other radiographic evaluation will be submitted to the Adjudication Committee for review (Section 5.3.2).

Details of data collection for adjudication of events will be provided in the adjudication charter.

## 9.6.1.2. Sympathetic Nervous System Dysfunction

Sympathetic nervous system dysfunction will be monitored throughout the study through physical examination, AE reporting, assessment of orthostatic hypotension, and the Survey of Autonomic Symptoms (Section 8.2.3.6). New onset or worsening of signs and symptoms of autonomic dysfunction will be evaluated by the investigator. Sympathetic nervous system dysfunction will only be diagnosed after consultation with an appropriate specialist, such as a neurologist and/or cardiologist.

In cases where new or worsening symptoms consistent with sympathetic nervous system dysfunction are moderate to severe or are clinically significant and do not resolve or return to baseline in 2 weeks (or less at the discretion of the investigator), study drug will be withheld and the patient will be referred to a specialist. If the evaluation by the appropriate specialist does not suggest sympathetic nervous system dysfunction, study drug may be restarted. If the specialist's evaluation does reveal sympathetic nervous system dysfunction then study drug will be permanently discontinued and the case reported as an AESI (Section 9.4.3).

Orthostatic hypotension may be a manifestation of sympathetic nervous system dysfunction. If a patient is determined to have orthostatic hypotension, study drug should be withheld and the AE should be entered in the electronic CRF (eCRF.). The following procedures should be followed:

- If the patient is symptomatic and a clinical explanation for orthostatic hypotension is identified (such as a new medication or dehydration due to exercise or illness or excessive heat exposure), study drug will be withheld, and the patient should return to the study site for an unscheduled visit in 1 to 10 days for an unscheduled assessment of orthostatic hypotension.
  - If the orthostatic hypotension has resolved, study drug may be restarted.
  - If the orthostatic hypotension has not resolved, then study drug will be withheld, and the patient will be referred to a specialist (neurologist or a cardiologist) for evaluation of sympathetic nervous system dysfunction.
  - If the specialist's evaluation does not reveal new onset sympathetic nervous system dysfunction, including symptoms of bradycardia (lightheadedness), orthostatic hypotension (lightheadedness on standing), syncope, absence of sweating in conditions where sweating would be expected, or if the specialist's evaluation identifies an alternative cause, such as initiation of a new medication known to cause orthostasis, then study drug may be given at the next visit.
  - If the specialist's evaluation does reveal sympathetic nervous system dysfunction, then study drug will be permanently discontinued and the case reported as an AESI (Section 9.4.3).
- If the patient has asymptomatic orthostatic hypotension, study drug will be withheld, and the patient should return to the study site for an unscheduled visit in 1 to 10 days for an unscheduled assessment of orthostatic hypotension.
  - If the unscheduled assessment does not reveal orthostatic hypotension then study drug may be continued.

- If the unscheduled assessment demonstrates orthostatic hypotension then study drug will continue to be withheld until the patient has been evaluated by a specialist (neurologist or a cardiologist) for evidence of sympathetic nervous system dysfunction.
- If the specialist's evaluation does not reveal new sympathetic nervous system dysfunction including symptoms of bradycardia (lightheadedness), orthostatic hypotension (lightheadedness on standing), syncope, absence of sweating in conditions where sweating would be expected, or if the specialist's evaluation identifies an alternative cause such as initiation of a new medication known to cause orthostasis, then study drug may be restarted.
- If the specialist's evaluation does reveal sympathetic nervous system dysfunction then study drug will be permanently discontinued and the case reported as an AESI (Section 9.4.3).

#### 9.6.1.3. Peripheral Sensory Adverse Events

Altered peripheral sensation (eg, paraesthesia and hypoaesthesia) is an important identified risk with fasinumab (see Investigator's Brochure) and other anti-NGF compounds. Any peripheral sensory AE that, per the investigator's judgment, requires a neurology or other specialty consultation must be reported as an AESI. If any peripheral sensory event persists for 2 months the patient must be referred for a neurology or other specialty consultation and the event must be reported as an AESI (Section 9.4.3).

## 9.6.1.4. Joint Replacement Surgery

An end of study phone contact will be conducted at 52 weeks following the last dose of study drug to evaluate the number of patients who have undergone or are scheduled for JR surgery as described in Section 8.2.3.9. Any elective JR surgery planned before completion of the ICF would be part of the exclusion criteria and would not be considered an AE.

After signing of the ICF, report JR surgery as an AESI if the JR surgery is an elective event that is not associated with a new/worsening AE.

Do not report JR surgery as an AE/AESI if the JR surgery is for the treatment of a new or worsening AE. In this case, the new or worsening AE should be the reported AE/AESI term.

# 9.7. Investigator Alert Notification

Regeneron (or designee) will inform all investigators participating in this clinical trial, as well as in any other clinical trial using the same investigational drug, of any SAE that meets the relevant requirements for expedited reporting (an AE that is serious, unexpected based on the Investigator's Brochure or this protocol, and has a reasonable suspected causal relationship to the medicinal/study drug).

#### 10. STATISTICAL PLAN

This section provides the basis for the statistical analysis plan (SAP) for the study. The SAP may be revised during the study to accommodate amendments to the clinical study protocol and to make

changes to adapt to unexpected issues in study execution and data that may affect the planned analyses. The final SAP will be issued before the database is locked.

Analysis variables are listed in Section 1.

## 10.1. Statistical Hypothesis

There are 29 hypotheses for the primary and key secondary endpoints. The primary treatment comparison for the WOMAC pain and physical function subscale scores is declared superior only if the comparisons are significant for both WOMAC pain and physical function subscale scores. The graphical testing procedure (Bretz 2009) will be applied to control for multiplicity and to maintain study-wise Type I error rate at two-sided 0.05 level for the two sets of hypotheses ( $H_{1,i}$ , i=1,...,16 for fasinumab 1 mg Q4W, and  $H_{2,i}$ , i=1,...,13 for fasinumab 1 mg Q8W) for the primary and key secondary endpoints. If a hypothesis is rejected, the alpha level for that hypothesis will be reallocated to other hypothesis according to a pre-specified procedure. The testing will stop when no hypothesis can be rejected at any step. Details will be provided a priori in the SAP.

- H1,1: There is no treatment difference between fasinumab 1 mg Q4W and placebo in WOMAC pain or physical function subscale scores at week 16 versus there is treatment difference in WOMAC pain and physical function subscale scores at week 16
- H1,2: There is no treatment difference between fasinumab 1 mg Q4W and placebo in Patient Global Assessment score at week 16 versus there is treatment difference in Patient Global Assessment score at week 16
- H1,3: There is no treatment difference between fasinumab 1 mg Q4W and placebo in the proportion of patients with ≥30% improvement in the WOMAC pain subscale scores at week 16 versus there is treatment difference in proportion of patients with ≥30% improvement in WOMAC pain at week 16
- H1,4: There is no treatment difference between fasinumab 1 mg Q4W and naproxen in the WOMAC pain subscale scores at week 16 versus there is treatment difference in WOMAC pain subscale scores at week 16
- H1,5: There is no treatment difference between fasinumab 1 mg Q4W and naproxen in the WOMAC physical function subscale scores at week 16 versus there is treatment difference in WOMAC physical function subscale scores at week 16
- H1,6: There is no treatment difference between fasinumab 1 mg Q4W and placebo in WOMAC pain subscale scores at week 44 versus there is treatment difference in WOMAC pain subscale scores at week 44
- H1,7: There is no treatment difference between fasinumab 1 mg Q4W and placebo in WOMAC physical function subscale scores at week 44 versus there is treatment difference in WOMAC physical function subscale scores at week 44
- H1,8: There is no treatment difference between fasinumab 1 mg Q4W and placebo in Patient Global Assessment score at week 44 versus there is treatment difference in Patient Global Assessment score at week 44

- H1,9: There is no treatment difference between fasinumab 1 mg Q4W and naproxen in Patient Global Assessment score at week 16 versus there is treatment difference in Patient Global Assessment score at week 16
- H1,10: There is no treatment difference between fasinumab 1 mg Q4W and placebo in the WOMAC pain subscale scores averaged across weeks 4, 8, 12 and 16 versus there is treatment difference in the WOMAC pain subscale scores averaged across weeks 4, 8, 12 and 16
- H1,11: There is no treatment difference between fasinumab 1 mg Q4W and placebo in the WOMAC physical function subscale scores averaged across weeks 4, 8, 12 and 16 versus there is treatment difference in the WOMAC physical function subscale scores averaged across weeks 4, 8, 12 and 16
- H1,12: There is no treatment difference between fasinumab 1 mg Q4W and placebo in the WOMAC pain subscale scores averaged across weeks 36, 40 and 44, versus there is treatment difference in the WOMAC pain subscale scores averaged across weeks 36, 40 and 44
- H1,13: There is no treatment difference between fasinumab 1 mg Q4W and placebo in the WOMAC physical function subscale scores averaged across weeks 36, 40 and 44, versus there is treatment difference in the WOMAC physical function subscale scores averaged across weeks 36, 40 and 44,
- H1,14: There is no treatment difference between fasinumab 1 mg Q4W and naproxen in WOMAC pain subscale scores at week 44 versus there is treatment difference in WOMAC pain subscale scores at week 44
- H1,15: There is no treatment difference between fasinumab 1 mg Q4W and naproxen in WOMAC physical function subscale scores at week 44 versus there is treatment difference in WOMAC physical function subscale scores at week 44
- H1,16: There is no treatment difference between fasinumab 1 mg Q4W and naproxen in the proportion of patients with ≥30% improvement in the WOMAC pain subscale scores at week 16 versus there is treatment difference in proportion of patients with ≥30% improvement in WOMAC pain at week 16
- H2,1: There is no treatment difference between fasinumab 1 mg Q8W and placebo in WOMAC pain or physical function subscale scores at week 16 versus there is treatment difference in WOMAC pain and physical function subscale scores at week 16
- H2,2: There is no treatment difference between fasinumab 1 mg Q8W and placebo in Patient Global Assessment score at week 16 versus there is treatment difference in Patient Global Assessment score at week 16
- $H_{2,3}$ : There is no treatment difference between fasinumab 1 mg Q8W and placebo in the proportion of patients with  $\geq 30\%$  improvement in the WOMAC pain subscale scores at week 16 versus there is treatment difference in proportion of patients with  $\geq 30\%$  improvement in WOMAC pain at week 16

- H2,4: There is no treatment difference between fasinumab 1 mg Q8W and naproxen in the WOMAC pain subscale scores at week 16 versus there is treatment difference in WOMAC pain subscale scores at week 16
- H2,5: There is no treatment difference between fasinumab 1 mg Q8W and naproxen in the WOMAC physical function subscale scores at week 16 versus there is treatment difference in WOMAC physical function subscale scores at week 16
- H2,6: There is no treatment difference between fasinumab 1 mg Q8W and placebo in WOMAC pain subscale scores at week 44 versus there is treatment difference in WOMAC pain subscale scores at week 44
- H2,7: There is no treatment difference between fasinumab 1 mg Q8W and placebo in WOMAC physical function subscale scores at week 44 versus there is treatment difference in WOMAC physical function subscale scores at week 44
- H2,8: There is no treatment difference between fasinumab 1 mg Q8W and placebo in Patient Global Assessment score at week 44 versus there is treatment difference in Patient Global Assessment score at week 44
- H2,9: There is no treatment difference between fasinumab 1 mg Q8W and naproxen in Patient Global Assessment score at week 16 versus there is treatment difference in Patient Global Assessment score at week 16
- H2,10: There is no treatment difference between fasinumab 1 mg Q8W and placebo in the WOMAC pain subscale scores averaged across weeks 4, 8, 12 and 16 versus there is treatment difference in the WOMAC pain subscale scores averaged across weeks 4, 8, 12 and 16
- H2,11: There is no treatment difference between fasinumab 1 mg Q8W and placebo in the WOMAC physical function subscale scores averaged across weeks 4, 8, 12 and 16 versus there is treatment difference in the WOMAC physical function subscale scores averaged across weeks 4, 8, 12 and 16
- H2,12: There is no treatment difference between fasinumab 1 mg Q8W and placebo in the WOMAC pain subscale scores averaged across weeks 36, 40 and 44 versus there is treatment difference in the WOMAC pain subscale scores averaged across weeks 36, 40 and 44
- H2,13: There is no treatment difference between fasinumab 1 mg Q8W and placebo in the WOMAC physical function subscale scores averaged across weeks 36, 40 and 44 versus there is treatment difference in the WOMAC physical function subscale scores averaged across weeks 36, 40 and 44

# **10.2.** Justification of FAS and mFAS Sample Sizes

In this study, approximately 2560 patients were to be randomized to fasinumab 1 mg SC Q4W (840), fasinumab 1 mg SC Q8W (600), naproxen (840), or placebo (280) (see Section 5.1.3). This sample size was expected to provide adequate power for the comparisons between fasinumab and naproxen at week 16 for the WOMAC pain and physical function scores and the PGA score and provide long term data for safety assessment.

The sample size for the full analysis set (FAS) population was based on results of the WOMAC pain and physical function subscale scores and the PGA from the R475-PN-1227 study. The calculation of sample size assumed a 2-sided alpha level of 0.025 and a 15% dropout rate up to week 16 and a 30% dropout rate up to week 52. Enrollment of 840 patients in the fasinumab 1 mg Q4W group and 280 patients in the placebo group would have provided at least 99% power to detect an effect size of 0.46 in the WOMAC pain and physical function subscale scores (ie, an absolute treatment difference of 1.1 between fasinumab and placebo and a standard deviation [SD] of 2.4 at week 16 and 52 for the FAS). This sample size would have provided 99% power to detect an effect size of 0.36 in PGA for an absolute treatment difference of 0.4 with an SD of 1.1 at week 16, and 98% power at week 52 for the FAS.

For the fasinumab 1 mg Q8W group, the 600 patients in the FAS population were to be compared to approximately 200 patients in the placebo group who were enrolled after amendment 5 global was implemented. For such comparisons, 2-sided alpha level of 0.025 and a 15% dropout rate up to week 16 and a 30% dropout rate up to week 52 were assumed. Additionally, the effect size for such comparisons was assumed to be 80% of the effect size for the comparison between fasinumab 1 mg Q4W group and the placebo group. Under these assumptions, enrollment of 600 patients in the fasinumab 1 mg Q8W group and 200 patients from the placebo group would have provided 97% power to detect an effect size of 0.368 (=0.46\*80%) in the WOMAC pain and physical function subscale scores at week 16 and 93% power at week 52. This sample size would have provided 84% power to detect an effect size of 0.288 (=0.36\*80%) in PGA at week 16, and 75% power at week 52 for the FAS.

The sample size calculation was also based on previously reported results of the WOMAC pain subscale and physical function subscale and the PGA for naproxen (Ekman 2014) (Schnitzer 2015). Assuming a 2-sided alpha level of 0.025 and a 15% dropout rate up to week 16 and a 30% dropout rate up to week 52, an enrollment of 840 patients in the fasinumab 1 mg Q4W group and the naproxen group would have provided at least 97% power to detect an effect size of 0.22 in the WOMAC pain subscale (ie, an absolute treatment difference of 0.51 with an SD of 2.3) at week 16, and 92% power at week 52 for FAS. This sample size would have provided 98% power to detect an effect size of 0.24 in WOMAC physical function subscale (ie, absolute treatment difference of 0.50 with an SD of 2.1) at week 16, and 96% power at week 52 for FAS. This sample size would have provided 87% power to detect an effect size of 0.18 in PGA at week 16 between fasinumab 1 mg Q4W and naproxen for the FAS.

Due to regional irregularities noted in a parallel phase 3 study that became fully apparent only after unblinding that study, and the concern that the same irregularities would be present in data from similar sites in this study, the population for the primary and secondary efficacy analyses was changed in Protocol Amendment 8 to be based on a modified full analysis set (mFAS) that excludes the randomization stratum for that region. Based on the assumptions above, it is estimated that this mFAS will provide:

 99.9% power to detect a significant difference between the 1 mg Q4W group and the placebo group in the WOMAC pain and physical function subscales at an alpha level of 0.05

- 42% and 46% power to detect a significant difference between the 1 mg Q8W group and the placebo group in WOMAC pain and physical function subscales, respectively, at an alpha level of 0.01
- 99.9% power to detect a significant difference between the 1 mg Q4W group and the naproxen group in the WOMAC pain and physical function subscales at an alpha level of 0.04

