#### 10.3.2. Modified Full Analysis Set

Due to regional irregularities noted in a parallel phase 3 study that became fully apparent only after unblinding that study, and the concern that the same irregularities would be present in data from similar sites from the same region in this study, the primary and secondary efficacy analyses will be performed on an mFAS. This mFAS is comprised of the FAS excluding patients from the region of concern (Rest of the World stratum). Efficacy and patient-reported outcome endpoints will be analyzed using the mFAS including patients randomized to fasinumab 1 mg Q4W, fasinumab 1 mg Q8W, naproxen, and placebo. For the analysis of fasinumab 1 mg Q8W group comparing to the control groups, only the subset of patients concurrently randomized (ie, after Protocol R475-OA-1611 Amendment 5 Global was implemented) will be included.

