### **1.2.4. Revision History for SAP Amendments**

This is the second version of the SAP based on Protocol Amendment 8 Global. The original version was approved and dated 23APR2020 based on Protocol Amendment 7 Global. This version includes an additional analysis population in Section 3, the Modified Full Analysis Set (mFAS). Due to regional irregularities noted in a parallel phase 3 study that became fully

apparent only after unblinding that study, and the concern that the same irregularities would be present in data from similar sites in this study, the primary and secondary efficacy analysis will be performed on a modified Full Analysis Set that excludes patients in the randomization stratum from the region of concern. Analyses using the FAS will also be provided.

Wording was added to Section 2.2 to quantify how the power was impacted by changing the primary analysis population from the FAS to the mFAS.

[figure not shown]
The method used to address imputed values that are implausible (Section 5.7.1) was also updated.

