The sample size calculation was also based on previously reported results of the WOMAC pain subscale and physical function subscale and the PGA for naproxen (Ekman 2014) (Schnitzer 2015). Assuming a 2-sided alpha level of 0.025 and a 15% dropout rate up to week 16 and a 30% dropout rate up to week 52, an enrollment of 840 patients in the fasinumab 1 mg Q4W group and the naproxen group would have provided at least 97% power to detect an effect size of 0.22 in the WOMAC pain subscale (i.e., an absolute treatment difference of 0.51 with a SD of 2.3) at week 16, and 92% power at week 52 for FAS. This sample size would have provide 98% power to detect an effect size of 0.24 in WOMAC physical function subscale (i.e., absolute treatment difference of 0.50 with a SD of 2.1) at week 16, and 96% power at week 52 for FAS. This sample size would have provided 87% power to detect an effect size of 0.18 in PGA at week 16 between fasinumab 1 mg Q4W and naproxen for the FAS.

While the number of patients randomized was based on the sample size calculations in the protocol, the analyses of the primary and secondary efficacy endpoints will be performed at levels of significance as specified in Section 5.7.4 of this document which differs than the initial assumptions used above.

Due to regional irregularities noted in a parallel phase 3 study, the population for the primary and secondary efficacy analyses was changed in Protocol Amendment 8 Global to be performed on a modified Full Analysis Set (mFAS) that excludes patients in the randomization stratum for that region. Based on the number of patients randomized and the testing strategy specified in Section 5.7.4 it is estimated that this mFAS will provide:

- 99.9% power to detect a statistically significant difference between the 1 mg Q4W group and the placebo group in the WOMAC pain and physical function subscales at Week 16 using an alpha level of 0.05.
- 42% and 46% power to detect a statistically significant difference between the 1 mg Q8W group and the placebo group in WOMAC pain and physical function subscales, respectively, at Week 16 using an alpha level of 0.01.
- 99.9% power to detect a statistically significant difference between the 1 mg Q4W group and the naproxen group in the WOMAC pain and physical function subscales at Week 16 using an alpha level of 0.04.

As the analysis for Year 2 will be descriptive only, a targeted sample size based on power considerations was not implemented for Year 2.

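### The mFAS powers in protocol 10.2 are attributed to the stated planning assumptions, but no single mFAS size reproduces them under those assumptions

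*Protocol*

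**What the plan says.** Protocol 10.2 first gives the FAS planning assumptions:

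- arms of 840 (Q4W), 600 (Q8W), 840 (naproxen) and 280 (placebo);
- about 200 placebo patients enrolled after Amendment 5 as the comparator for Q8W;
- 15% dropout to week 16 and a two-sided alpha of 0.025;
- standardized effects of 0.46 for Q4W vs placebo on both WOMAC subscales, and 0.22 (pain) and 0.24 (function) for Q4W vs naproxen.

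For Q8W vs placebo it adds: "Additionally, the effect size for such comparisons was assumed to be 80% of the effect size" for Q4W vs placebo, which is 0.368 for both subscales.

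The section then turns to the mFAS, the FAS without the Rest of the World stratum. The lead-in is "Based on the assumptions above, it is estimated that this mFAS will provide". The bullets are 99.9% for Q4W vs placebo at alpha 0.05; "42% and 46% power to detect a significant difference between the 1 mg Q8W group and the placebo group" (pain and function, alpha 0.01); and "99.9% power to detect a significant difference between the 1 mg Q4W group and the naproxen group" (both subscales, alpha 0.04). The synopsis has the same lead-in and figures. Under protocol 10.3.2, for Q8W against the controls "only the subset of patients concurrently randomized (ie, after Protocol R475-OA-1611 Amendment 5 Global was implemented) will be included".

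SAP 2.2 states the same powers, for week 16, but opens with "Based on the number of patients randomized and the testing strategy specified in" its Section 5.7.4. It also says that testing uses "levels of significance as specified in Section 5.7.4 of this document which differs than the initial assumptions used above". SAP 1.2.4 describes the added text as there "to quantify how the power was impacted by changing the primary analysis population" from FAS to mFAS. SAP 1.2.3 declares no modifications from the protocol's statistical section.

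**The concern.** These are the only powers given for the population on which the primary and secondary efficacy analyses are run. The lead-in invites the reader to derive them from the preceding paragraphs, and that cannot be done. Two of the three bullets conflict with each other under the stated effects, and the protocol and SAP name different bases for identical figures.

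What is at stake is interpretation. A reader of the protocol lead-in and SAP 1.2.4 would attribute the fall in Q8W power, from 97% to under 50%, mainly to excluding one region. SAP 2.1 identifies that stratum as South Africa alone; its enrolment is not given. If a smaller Q8W effect than the stated 80% was in fact assumed, that bears on how a negative Q8W result is read, and the documents should say so.

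**Working it through.** **Method.** Two-sample comparison of means, SD scaled to 1, noncentral t with n1+n2-2 degrees of freedom and noncentrality d x sqrt(n1 x n2/(n1+n2)), two-sided. Evaluable n = planned n x 0.85: 714/238 for Q4W vs placebo, 510/170 for Q8W vs placebo, 714/714 for Q4W vs naproxen.

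**Step 1: reproduce the plan's FAS powers (alpha 0.025, week 16).**

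| Comparison | Recomputed | Stated |
|---|---|---|
| Q4W vs placebo, WOMAC (0.46) | >99.9% | at least 99% |
| Q4W vs placebo, PGA (0.36) | 99.5% | 99% |
| Q8W vs placebo, WOMAC (0.368) | 97.2% | 97% |
| Q8W vs placebo, PGA (0.288) | 84.2% | 84% |
| Q4W vs naproxen, pain (0.22) | 97.2% | at least 97% |
| Q4W vs naproxen, function (0.24) | 98.9% | 98% |
| Q4W vs naproxen, PGA (0.18) | 87.6% | 87% |

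All agree to within about 1 point, so the method matches the plan's.

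**Step 2: same inputs, mFAS alphas, whole planned FAS.**

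- Q4W vs placebo, alpha 0.05: >99.9%.
- Q8W vs placebo, alpha 0.01: noncentrality 0.368 x sqrt(510 x 170/680) = 0.368 x 11.29 = 4.155. The normal approximation gives Phi(4.155 - 2.576) = 94.3%; noncentral t gives 94.2%. The figure is the same for pain and function.
- Q4W vs naproxen, alpha 0.04: noncentrality 0.22 x sqrt(357) = 4.157 and 0.24 x sqrt(357) = 4.535. Phi(4.157 - 2.054) = 98.2% and Phi(4.535 - 2.054) = 99.3%.

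The change of alpha from 0.025 to 0.01 therefore takes Q8W only from 97.2% to 94.2%.

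**Step 3: two powers from one effect.** With d = 0.368, one sample, one dropout rate and one alpha, pain and function must have equal power. The plan states 42% and 46%. This needs no assumption about the size of the mFAS.

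**Step 4: can a smaller mFAS explain the set?** Solving for the share f of planned post-Amendment 5 patients:

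- 42% needs f = 0.331 (about 199/66 randomized, 169/56 evaluable);
- 46% needs f = 0.360 (about 216/72 randomized, 183/61 evaluable).

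Q4W vs naproxen at those shares:

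- both cohorts shrink alike: 63.1-66.8% (pain), 70.9-74.6% (function);
- all planned pre-Amendment 5 patients kept (240 per arm, protocol 5.1.3): (240 + 600f) x 0.85 = 373-387 evaluable per arm, giving 82.8-84.2% and 88.9-90.0%.

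The stated figure is 99.9% for both. The share retained is not in the documents, so a range is shown (naproxen pain / naproxen function / Q8W, in %):

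| Share kept | Both cohorts shrink | Only later cohort shrinks |
|---|---|---|
| 100% | 98 / 99 / 94 | 98 / 99 / 94 |
| 90% | 97 / 99 / 91 | 97 / 99 / 91 |
| 70% | 92 / 96 / 81 | 95 / 98 / 81 |
| 50% | 81 / 87 / 64 | 90 / 94 / 64 |
| 33-36% | 63-67 / 71-75 / 42-46 | 83-84 / 89-90 / 42-46 |

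**Step 5: more patients than planned?** At alpha 0.04, 99.9% needs 1,094 (pain) or 920 (function) evaluable per arm, which at 15% dropout is about 1,288 or 1,082 randomized, against 840 planned. Extra post-Amendment 5 patients would also raise Q8W power. Extra pre-Amendment 5 patients would not, but with all 600 later patients kept there would have to be 1,288 - 600 = 688 or 1,082 - 600 = 482 per arm, against an estimated 240.

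**Step 6: Q4W vs placebo.** If both cohorts shrink alike, 99.9% at alpha 0.05 fits retention of about 68% or more. At that point Q8W is 79.7% and naproxen 91.4%/95.3%.

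**The case against.** The strongest reply is that the mFAS is a subset of the FAS, so a Q8W power below 94% is expected, and that SAP 2.2 already says the significance levels changed and that the number randomized was used. Both points stand. A reader might infer that 94% against 42/46% is a contradiction in itself; it is not, because 94% is only an upper bound at the planned numbers. The conflict lies in the two unequal Q8W powers and in the Q8W and naproxen bullets taken together. The disclosed changes do not resolve it: the stated alphas are used throughout the check, and no number of patients near the plan reconciles the bullets.

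It is also fair that the naproxen bullet alone is weak evidence. At the full planned numbers the gaps are 1.7 and 0.6 points, and with zero dropout the powers would be 99.3% and 99.8%.

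A further tempting inference is that Q8W was secretly assumed to have about half the Q4W effect. The documents do not support that. The Q8W effect that would give 42-46% is 0.21-0.22 if everyone is retained (46-48% of 0.46), 0.25-0.26 at 70% retained and 0.30-0.31 at 50% (about two thirds of 0.46), and the share retained is unknown.

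Finally, these powers drive no sample size, test, interim or futility rule, and a Q8W result will be read from its estimate, interval and p-value. That stands, and it limits the consequence to reporting.

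**Conclusion.** The point holds as a reporting error. Under the effects, dropout and planned arm sizes that the lead-in refers to, no single mFAS size yields 42%/46% for Q8W vs placebo together with 99.9% for Q4W vs naproxen. At the retention that gives the Q8W figures, naproxen falls short by roughly 33-37 points (pain) and 25-29 points (function) if both cohorts shrink alike, and by about 16-17 and 10-11 points if every planned pre-Amendment 5 patient is kept.

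This rests on the planned numbers (with 240 per arm before Amendment 5, itself an estimate), 15% dropout and a standard two-sample calculation that matches the plan's week-16 FAS powers. The size of the excluded stratum is treated as unknown.

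A reader might go further and conclude that the stated powers are wrong, or that the analysis is compromised. The documents show neither. The powers may be right for inputs that are not disclosed, and different inputs were probably used, but the text does not say which. Confidence in the mismatch is high.

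**What to change.** In the synopsis, protocol 10.2 and SAP 2.2, do one of two things, with the same basis wording in all three places:

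- recompute the three bullets under the stated assumptions with the actual mFAS numbers; or
- replace the lead-in with the inputs actually used: mFAS patients per arm (total and post-Amendment 5), effect and SD for each subscale, dropout, and the source of each.

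If the Q8W effect was revised from 80% of the Q4W effect, say so there. The cost is a text change only. No alpha, endpoint, analysis set, model or testing procedure changes, though some stated figures may become less favourable.
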